5.3 Handling of Missing Data

All attempts will be made to limit the amount of missing data. Unless otherwise specified, no attempt will be made to impute missing data. If a data point is missing, that data point will not contribute to that portion of the analysis. The number of evaluable observations will be reported in analysis so that extent of missing data can be assessed.

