8.4.2. EFFECTIVENESS ENDPOINT

Descriptive statistics will be used to describe the effectiveness measures.

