5.2 Analysis Populations

Primary Analysis population: The primary safety and effectiveness analyses will be based on data from all enrolled subjects in this post approval study (ITT, Intention-to-treat).

Per-Protocol Safety Analysis Population: A per-protocol (PP) population will be identified based on those subjects who met the original inclusion and exclusion criteria, have demonstrated substantial compliance with the protocol and no significant protocol deviations affecting the primary endpoints. Supportive analyses for the primary effectiveness endpoint and all secondary and exploratory analyses will be performed in the PP population.

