5.6.2.1 Primary Analysis

Effectiveness will be measured as percentage change in the percent time in range (based on hours) at one month post-first sensor insertion compared to 12 months post-first sensor insertion using a time in range definition of glucose values between 70 mg/dL and 180 mg/dL. The Time in Range will be summarized as the mean of the subject percentages, together with the median, standard deviation, minimum, maximum, and 25th / 75th percentiles.

Summary statistics will also be provided for the change in HbA1c levels from baseline, and average hours of use per day.

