5.6.2.2 Sensitivity Analysis

Sensitivity analyses for the primary safety endpoint will be performed including:

- Analysis using the PP safety analysis population

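### The primary effectiveness analysis is labelled ITT in all enrolled subjects, but under the SAP's own rules the month-1 to month-12 change in time in range is a complete-case result

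*SAP*

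**What the plan says.** **Population.** SAP 5.2, like Protocol 8.1, states: "The primary safety and effectiveness analyses will be based on data from all enrolled subjects in this post approval study (ITT, Intention-to-treat").

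**Endpoint and summary.** SAP 5.6.2.1 measures effectiveness as "percentage change in the percent time in range (based on hours) at one month post-first sensor insertion compared to 12 months post-first sensor insertion". It then says: "The Time in Range will be summarized as the mean of the subject percentages", with the usual distributional statistics. It gives no model, confidence interval or missing-data method. Protocol 8.4.2 confirms the status of the endpoint: "Descriptive statistics will be used to describe the effectiveness measures".

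**Missing data.** SAP 5.3: "Unless otherwise specified, no attempt will be made to impute missing data". It continues: "If a data point is missing, that data point will not contribute to that portion of the analysis". The safeguard offered is a count: "The number of evaluable observations will be reported in analysis so that extent of missing data can be assessed". SAP 5.4 adds visit accountability and early exits by reason.

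**Sensitivity.** SAP 5.6.2.2 lists one item, "Analysis using the PP safety analysis population". Its lead-in sentence names the safety endpoint, although the section belongs to effectiveness.

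**The concern.** The label and the rule describe different sets of people. An ITT label tells the reader that the figure speaks for everyone enrolled. The default in SAP 5.3, with nothing in 5.6.2.1 to override it, restricts the change to subjects observed in both months.

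Subjects can fall out in several ways:
- Withdrawal is open at any time (Protocol 4.3).
- CGM data reach the sponsor only if the subject synchronizes them (Protocol 7.3), so an active subject who does not wear or synchronize the device is lost too.
- Participation may end once the study-wide cycle target is met (Protocol synopsis), possibly before a late enrollee reaches month 12.

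The study has one arm, so no control group would reveal selection. If subjects without month 12 differ in how their glucose control changes, the contrast mixes real change with a change in who is measured. This is the primary endpoint for the objective of demonstrating long-term effectiveness. HbA1c change at each 6-month point (SAP 5.6.4) falls under the same default.

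**Working it through.** **1. Is there a plan figure to reproduce?** Not for effectiveness: there is no sample size, power, threshold or dropout rate. The only powered analysis is the safety test, which this point does not touch.

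**2. What enters the result?** Setting the sections side by side:
- 5.2: all enrolled subjects.
- 5.6.2.1: a within-subject change, which needs month 1 and month 12.
- 5.3: a missing value is left out of the part of the analysis that needs it.

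A subject without month 12 has no change value and is left out. That subject's month-1 value could still enter a stand-alone month-1 summary. If two monthly means were then compared, they would cover different subjects.

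**3. Can the label hold with full retention?** Up to 400 are enrolled in order to insert 273 (SAP 3). Up to 400 − 273 = 127 enrolled subjects (127/400 = 32%) may never have a Sensor and so can have no time in range. This bears on the label only.

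**4. Do 273 subjects and 1400 cycles imply a retention rate?** No. 1400/273 = 5.1 cycles per subject, but a full 24 months is 8 cycles on 90-day Sensors and 4 on 180-day Sensors.
- All on 90-day Sensors with 10% loss per cycle: 273 × (0.9 + 0.9² + … + 0.9⁸) = 273 × 5.126 ≈ 1399.
- Mixed Sensors with no loss: 77 × 8 + 196 × 4 = 616 + 784 = 1400.

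Both fit, so the target says nothing about dropout.

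**5. Size under stated assumptions.** Let r be the share of the 273 inserted subjects with month-12 data (all assumed to have month 1). Let g be the mean change in those with month 12 minus the mean change in those without.

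Complete-case mean − mean in all inserted = (1 − r) × g.

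If subjects with month 12 gained 2 points on average (assumed), the mean over all inserted is zero when the others changed by −2r/(1 − r).

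| Lacking month 12 (assumed) | Evaluable of 273 | Share of 400 | Error, g = 5 | Error, g = 10 | Change in the others that cancels +2 |
|---|---|---|---|---|---|
| 10% | 246 | 61.5% | 0.5 | 1.0 | −18 |
| 20% | 218 | 54.5% | 1.0 | 2.0 | −8 |
| 30% | 191 | 47.8% | 1.5 | 3.0 | −4.7 |
| 40% | 164 | 41.0% | 2.0 | 4.0 | −3 |

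Errors are in percentage points of time in range. The formula also holds on the SAP's percentage-change scale, with g expressed on that scale.

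**6. Against sampling error.** With an assumed SD of change of 10 to 15 points, the 95% half-width is 1.96 × SD/√n. It is 1.2 to 1.9 points at n = 246 and 1.5 to 2.3 at n = 164. With g = 5, the error (0.5) is well below the half-width at 10% missing and about equal to it (2.0) at 40%.

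**The case against.** The strongest reply is that nothing formal depends on this endpoint. It is descriptive, it has no hypothesis or margin, and the only test in the study is the safety test. SAP 5.3 and 5.4 already promise evaluable counts, reasons for exclusion, accountability by visit and exits by reason, so a reader will see how much is missing. This stands, and it limits the severity. It does not answer the point: counts show the extent of missing data without adjusting the estimate or showing whether the missing subjects differ.

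A second reply is that subjects never inserted cannot have a value under any method, because the endpoint is dated from first insertion and measured by the device. This also stands. The gap of up to 127 calls for a corrected label and is no evidence of bias.

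Third, a reader might infer from 273 subjects and 1400 cycles that about 10% are lost per 90-day cycle, leaving 0.9⁴ = 66%, or 179 subjects, at month 12. The documents do not support this, since the same total arises with no dropout under a mix of Sensors.

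Fourth, a reader might assume that leavers do worse, so that the result must look too good. That is plausible for an implanted device, but neither document says so. Loss through failed synchronization, or through the cycle target being met, could work either way.

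**Conclusion.** The mismatch between label and analysis is certain from the text. The primary effectiveness result is a complete-case summary in subjects with CGM data in both months, presented as ITT in all enrolled subjects, and no planned analysis tests how far it depends on who was observed. The per-protocol analysis narrows the set further.

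The consequence is possible bias in a descriptive estimate, with no effect on type I error or power. Its size and direction cannot be settled from the documents. The range of 0.5 to 2.0 points rests on an assumed 10% to 40% of inserted subjects lacking month 12 and an assumed 5-point gap; it doubles if the gap is 10 points and reverses sign if the gap does. Two stronger inferences, that the result is known to be inflated or that about a third of inserted subjects will be missing, go beyond what the plan supports. This is a should-fix item and a cheap improvement.

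**What to change.** Amend the SAP before the final analysis:

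1. In 5.2 and 5.6.2.1, name the set for the complete-case summary as inserted subjects with month-1 and month-12 CGM data, state the minimum amount of data that makes a month evaluable, and stop calling this summary ITT.
2. In 5.6.2.1, keep the planned percentage-change summary. Beside it, fit a mixed model for repeated measures to monthly time in range, months 1 to 12, in all inserted subjects with at least one month of data. Report month 12 minus month 1 in percentage points with a two-sided 95% CI. Synchronized readings from before exit are already in the DMS.
3. Add a delta-adjusted (tipping-point) analysis, because the model assumes data missing at random. Giving subjects without month 12 their own month-1 value would be a poor substitute: if the observed mean change is near zero, the estimate hardly moves, and the case in which the missing subjects do worse goes untested.
4. Tabulate baseline characteristics and month-1 time in range by month-12 availability.
5. Correct the endpoint named in the lead-in of 5.6.2.2.
6. Use the same repeated-measures approach for HbA1c change in 5.6.4.

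The cost is SAP wording and some programming, with no new data collection. The estimate may turn out less favourable than the complete-case figure.

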5.4 Subject Disposition

The number of subjects in each analysis population will be presented along with reason for any exclusions. Subject accountability will be summarized by visit. The number of subjects who are enrolled, eligible for follow-up, and number completing clinical follow-up will be summarized for each protocol-required visit. In addition, the number of subjects who complete the study or exit early will be summarized by reason.

5.5 Demographics and Baseline Characteristics

Descriptive statistics will be presented for all clinically relevant baseline demographic, medical history, and clinical characteristic variables.

5.6 Analysis of Study Endpoints

Statistical Analysis Plan		Page 8 of 11
Sponsor Senseonics	Study A Post Approval Study to Evaluate the Long-term Safety and Effectiveness of the Eversense® Continuous Glucose Monitoring (CGM) System	Version 1.0

5.6.1 Primary Safety Endpoint

The primary safety endpoint is the incidence of the composite of infection, secondary procedures to remove the Sensor, or procedure-related adverse events of at least moderate severity.

5.6.1.1 Primary Analysis

The primary safety composite endpoint will be evaluated in the following hypothesis, against a Performance Goal of 4%:

H0: The rate of the composite of infection, secondary procedures to remove the Sensor, or procedure-related adverse events of at least moderate severity (p) is greater than or equal to 4%.

$$H0: p \geq 4\%$$

H1: The rate of the composite of infection, secondary procedures to remove the Sensor, or procedure-related adverse events of at least moderate severity (p) is less than 4%.

$$H1: p < 4\%$$

The rate will be tested against the Performance Goal of 4%, using an exact, binomial test, with a one-sided p-value of 0.05 considered evidence of statistical significance. For the primary analysis, data will be analyzed on a per cycle basis, with each cycle contributing an independent observation.

The endpoint will be evaluated using the ITT analysis set.

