3.3. PRIMARY SAFETY HYPOTHESIS

The primary safety composite endpoint will be evaluated in the following hypothesis test against a Performance Goal of 4%:

H₀: The rate of the composite of infection, secondary procedures to remove the Sensor, or procedure-related adverse events of at least moderate severity (p) is greater than or equal to 4%.

$$H_0$$
: p ≥ 4%

H₁: The rate of the composite of infection, secondary procedures to remove the Sensor, or procedure-related adverse events of at least moderate severity (p) is less than 4%.

$$H_1$$
: p < 4%

The rate will be tested against the Performance Goal of 4%, using an exact, binomial test, with a one-sided p-value of 0.05 considered evidence of statistical significance. Data will be analyzed on a per cycle basis.

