4. STUDY POPULATION

The PAS will enroll up to 400 subjects (to insert 273 subjects) to ensure adequate numbers of subjects for the primary safety endpoint.

Senseonics, Inc. Confidential Information Protocol #: CTP-0034, Version 10

Page 17 of 43

Effective Date:#: 20 March

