8.4. SAMPLE SIZE JUSTIFICATION

8.4.1. PRIMARY SAFETY ENDPOINT:

A total of 1400 Sensor cycles contributing to the analysis is planned.

Based on data from the PRECISE (n=81 subjects), PRECISE II (n=90 subjects), PRECISION (n=35 subjects) and PMCF (n=1686 subjects) studies, a total of 31 events occurred that would meet the definition of the primary safety endpoint in this study. With a total of 1892 subjects, this equates to an observed rate of approximately 1.6% with an associated 95% confidence interval of 1.1% to 2.3%. As there is variability associated with this sample, as evidenced by the confidence interval, a conservative expected rate of events for this study is 2.3%. The planned sample size of 1400 total cycles) with this expected rate should provide greater than 95% power for the test of the performance goal of 4%.

Meeting the performance goal of 4% for the planned sample size would require a worst-case observation of a rate of approximately 3% or less (i.e., 41 or fewer events among 1400 cycles). This result will be clinically acceptable and similar to results observed in past studies.

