8.4.3. TOTAL ENROLLMENT AND FOLLOW-UP

At least 273 enrolled subjects will be inserted with Sensors to achieve at least 1400 Sensor cycles. Subjects will be encouraged to remain in the study up to 27 months of follow-up or after at least 1400 Sensor cycles are completed study wide.

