3.1 Blinding

There is no blinding in this study.

Statistical Analysis Plan		Page 6 of 11
Sponsor	Study	Version
Senseonics	A Post Approval Study to Evaluate the Long-term Safety and Effectiveness of the Eversense® Continuous Glucose Monitoring (CGM) System	1.0

4 Sample Size Determination

At least 273 enrolled subjects will be inserted with Sensors to achieve at least 1400 Sensor cycles. Subjects will be encouraged to remain in the study up to 27 months of follow-up or after at least 1400 Sensor cycles are completed study wide.

Based on data from the PRECISE (n=81 subjects), PRECISE II (n=90 subjects), PRECISION (n=35 subjects) and PMCF (n=1686 subjects) studies, a total of 31 events occurred that would meet the definition of the primary safety endpoint in this study. With a total of 1892 subjects, this equates to an observed rate of approximately 1.6% with an associated 95% confidence interval of 1.1% to 2.3%. As there is variability associated with this sample, as evidenced by the confidence interval, a conservative expected rate of events for this study is 2.3%. The planned sample size of 1400 total cycles) with this expected rate should provide greater than 95% power for the test of the performance goal of 4%.

Meeting the performance goal of 4% for the planned sample size would require a worst-case observation of a rate of approximately 3% or less (i.e., 41 or fewer events among 1400 cycles). This result will be clinically acceptable and similar to results observed in past studies.

5 Statistical Analyses

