5.6.1.2 Sensitivity Analysis

Sensitivity analyses for the primary safety endpoint will be performed including:

- Analysis using the PP safety analysis population.
- As an additional analysis, analysis will be performed using a logistic regression model fit via generalized estimating equations and a working compound symmetric covariance structure; this allows for the modeling of potential within-subject correlation. The model will consist of only an intercept term; estimates will be transformed to the proportion scale to facilitate comparisons to the primary analysis of the performance goal.
- An additional analysis will be performed based on only the first cycle for each subject. This will be based on an exact binomial method.

For each sensitivity analysis, the estimated endpoint rate and the associated one-sided 95% confidence interval will be calculated.

Statistical Analysis Plan		Page 9 of 11
Sponsor	Study	Version
Senseonics	A Post Approval Study to Evaluate the Long-term Safety and Effectiveness of the Eversense® Continuous Glucose Monitoring (CGM) System	1.0

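### The deciding primary safety test counts repeat sensor cycles in one subject as independent, and the printed limit of 41 events does not match its one-sided 0.05 rule, which allows 43

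*SAP*

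**What the plan says.** Protocol 3.3 and 8.2.1 and SAP 5.6.1.1 test the composite safety rate against a 4% goal with an exact binomial test, "with a one-sided p-value of 0.05 considered evidence of statistical significance". On the unit of analysis, SAP 5.6.1.1 (and protocol 8.2.1 in the same terms) states: "For the primary analysis, data will be analyzed on a per cycle basis, with each cycle contributing an independent observation".

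The cycles are repeated within subjects. Protocol 8.4.3 states: "At least 273 enrolled subjects will be inserted with Sensors to achieve at least 1400 Sensor cycles". Protocol section 4 caps enrolment at 400.

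The plan is aware of clustering. SAP 5.6.1.2 and protocol 8.2.1 add an intercept-only logistic GEE with an exchangeable working structure, noting that "this allows for the modeling of potential within-subject correlation". A further check is also planned: "An additional analysis will be performed based on only the first cycle for each subject". Both are additional or sensitivity analyses that report an estimate and a one-sided 95% bound. No rule says what follows if either disagrees with the primary test, and the type of GEE standard error is not given.

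Protocol 8.4.1 and SAP section 4 say that 1400 cycles at an expected 2.3% rate "should provide greater than 95% power for the test of the performance goal of 4"%, and that meeting the goal would need "41 or fewer events among 1400 cycles". Neither section uses an ICC or a design effect.

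**The concern.** This is the study's only formal hypothesis test. Positive correlation between cycles in the same subject widens the true sampling distribution of the event count, while the exact binomial test keeps the narrower one. The error therefore runs in the unsafe direction: a device at the 4% goal is declared below it too often. Protocol 5.4.2.4 alternates arms, which may weaken correlation for purely site-specific events. It does not remove subject-level causes such as healing or susceptibility to infection.

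The second problem is one of internal consistency. With 42 or 43 events among 1400 cycles, the test rule says the goal is met and the sample size text says it is not. That should be settled before the count is known.

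**Working it through.** **Inputs.** From the documents: null rate 4%; exact binomial, one-sided 0.05; 1400 cycles; at least 273 subjects inserted, at most 400 enrolled; expected rate 2.3%. Assumed: the ICC (none is given), the spread of cycles per subject, and exactly 1400 cycles.

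**1. The plan's own figures.** The prior-data rate reproduces: 31/1892 = 1.64%, exact 95% CI 1.12% to 2.32%. For the event limit, take X ~ Bin(1400, p):

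| Limit c | c/1400 | P(X ≤ c) at 4% | Power at 2.3% | One-sided 95% upper bound |
|---|---|---|---|---|
| 41 | 2.93% | 0.0203 | 94.7% | 3.78% |
| 43 | 3.07% | 0.0400 | 97.4% | 3.94% |
| 44 | 3.14% | 0.0545 | 98.2% | 4.02% |

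The largest count with p ≤ 0.05 is 43. At one-sided 0.025 the limit is 41, because P(X ≤ 42) = 0.0288. Poisson and normal versions at 0.05 also give 43, and Wald gives 44 or 45; none gives 41. The claim of more than 95% power is true for 43 and false for 41.

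**2. Clustering.** Mean cluster size is 1400/273 = 5.13, or 1400/400 = 3.5 if every enrolled subject were inserted. The variance inflation is approximately

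DE = 1 + (Σm²/Σm − 1) × ICC,

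where m is a subject's number of cycles. For near-equal clusters (238 subjects with 5 cycles, 35 with 6), Σm²/Σm = 5.15. At ICC 0.05, DE = 1 + 4.15 × 0.05 = 1.21, so the SD of the count rises from √(1400 × 0.04 × 0.96) = 7.33 to 8.06 around a mean of 56.

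The exact calculation convolves beta-binomial subject totals at a true 4% and takes P(X ≤ 43). Three mixes of 273 subjects were used, with Σm²/Σm of 5.15 (near-equal), 6.07 and 6.57 (1 to 8 cycles, increasingly uneven):

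| ICC | Type I error, 273 subjects |
|---|---|
| 0 | 4.0% |
| 0.02 | 4.6-4.8% |
| 0.05 | 5.5-6.1% |
| 0.10 | 7.1-8.1% |
| 0.20 | 9.9-11.7% |

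Recurrence risk after one event is 0.04 + ICC × 0.96: 8.8% at ICC 0.05, and 23.2% (5.8-fold) at 0.20, which is extreme.

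The 5% level is crossed at ICC 0.032, 0.027 and 0.024 for the three mixes. Sharper splits, such as 1 or 8 cycles, lower this to 0.021. A logit-normal model gives nearly the same thresholds. With 350 subjects the crossing is at 0.028-0.045 and with 400 at 0.030-0.052; the upper ends are near-equal clusters. If 41 were the operative limit, the 273-subject crossing would move to 0.10-0.13, so the two parts of this point interact.

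**3. Can the planned checks carry the decision?** First-cycle analysis, read as an exact test against 4%: with 273 subjects the limit is 5 events and power at 2.3% is 40%. With 400 subjects the limit is 9 and power 56%.

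GEE with sandwich standard errors on the logit scale, 273 subjects, 40,000 simulated trials per setting: type I error 4.6-5.7% over ICC 0 to 0.20. Power at 2.3% is 98% (ICC 0), 96-97% (0.02), 93.5-94.6% (0.05), 89-91% (0.10) and 80-82% (0.20).

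At a true 4%, the exact test passes while the GEE bound is not below 4% in 0.7-1.1% of trials at ICC 0.05, 2.0-2.7% at 0.10 and 4.6-6.0% at 0.20.

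**The case against.** The first part shows a conditional risk, not an established error. No ICC is documented, and the thresholds depend on assumed cycle mixes. Discreteness gives the exact test slack (4.0%), so it stays below 5% at ICC 0.02, and up to about 0.05 it differs little from the GEE, whose own error is only approximately 5%. The GEE and its bound are pre-specified, so any reader can compare that bound with 4%. No pass rule attaches to the first-cycle analysis, so its 40% power describes a test that the plan does not run.

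Changing the deciding test late in an unblinded study with interim reports invites the charge that the data drove the choice. The GEE is not immune either. With an assumed 30% withdrawal after an event and 4 to 8 planned cycles, its type I error was 5.8% at ICC 0.05 and 8.4% at 0.10.

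On the second part, the test rule is explicit and consistent, 41 is stricter than the rule, and the true limit moves with the final cycle count (44 at 1410, 45 at 1450).

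Most of this stands as a matter of weight. It does not remove the point. A bound that has no deciding role cannot change a pass. Under the same withdrawal assumption the exact test did worse (9.2% and 15.8%). A printed limit that belongs to a different alpha is wrong whichever way it errs.

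**Conclusion.** Both parts hold, and the plan should be corrected.

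The independence assumption exposes the only formal test to a type I error above 5% once the ICC passes about 0.024 to 0.032 with 273 subjects. That threshold reaches 0.052 only in the outer case of 400 near-equal subjects, and enrolled is not the same as inserted. The excess is negligible at ICC 0.02 or below, modest at 0.05 and clear from about 0.10. These figures rest on assumed ICCs, assumed cycle mixes, exactly 1400 cycles, and cycle counts unrelated to events.

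The 41-event limit contradicts the one-sided 0.05 rule with no such assumptions. The rule allows 43 of 1400, and the power claim printed beside 41 is true only for 43. The rule in SAP 5.6.1.1 governs, so the decision itself is not ambiguous to a careful reader, but the sample size text misdescribes it.

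**What to change.** - By a dated amendment before the end-of-study test, make the exchangeable GEE the deciding analysis in SAP 5.6.1.1 and protocol 3.3 and 8.2.1. Cluster on subject, specify robust (sandwich) standard errors, and declare the goal met if the one-sided 95% upper bound is below 4%. Keep the per-cycle and first-cycle exact tests as sensitivity analyses.
- In protocol 8.4.1 and SAP section 4, state that the quoted power assumes independent cycles, and give the GEE's power at 2.3% over an assumed ICC range.
- Correct the limit to 43 of 1400 for the exact one-sided 0.05 test, or restate alpha and power to match 41.
- If the sponsor keeps the exact test as deciding, say in advance how a pass with a GEE bound at or above 4% will be reported and interpreted.

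**Cost.** An amendment, for which SAP section 6 provides, and protocol wording; no new data. The bound will be somewhat wider, the stated power less favourable, and the type I error only approximately 5% (allow for about 6%, and more if withdrawal follows events). Because the study is unblinded, the change must be justified on the design and not on the observed rate. The 41/43 correction carries no such risk.
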